6.2.5 Serious Adverse Events

A Serious Adverse Event (SAE) is any untoward medical occurrence which:

- Results in death;
- Is life-threatening;
- Requires in-patient hospitalization for > 24 hours or prolongation of hospitalization which is not specifically required by the protocol;
- Results in permanent impairment of a body function or permanent damage to a body structure; or
- Requires medical or surgical intervention to preclude permanent impairment of a body function or permanent damage to a body structure.

6.2.6 Unanticipated Adverse Device Effect

An unanticipated adverse device effect (UADE) is “any serious adverse effect on health or safety or any life-threatening problem or death caused by, or associated with, a device, if that effect, problem, or death was not previously identified in nature, severity, or degree of incidence in the investigational plan or application (including a supplementary plan or application), or any other unanticipated serious problem associated with a device that relates to the rights, safety, or welfare of subjects” [FDA 21 CFR 812.3(s)]. The Sponsor will promptly conduct an investigation upon notification by an Investigator of a UADE. The competent authority, all reviewing Ethic Committees and participating Investigators will be notified within 10 working days after the sponsor first receives notice of the effect. Thereafter, the Sponsor will submit such additional reports concerning the effect as requested.

For the purposes of this study, only unanticipated adverse device effects will be reported promptly following occurrence. Annual progress reports will contain information regarding SAE/AE occurrences.

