6.2 Adverse Events (AE)

6.2.1 Definitions

Term	Definition
Adverse Event (AE)	
Any untoward medical occurrence, unintended disease or injury, or untoward clinical signs (including abnormal laboratory findings) in subjects, users or other persons, whether or not related to the medical device used in the investigation.
 
NOTE 1: This definition includes events related to the investigational medical device or the comparator.
 
NOTE 2: This definition includes events related to the procedures involved.

Adverse Event of Special Interest (AESI)	
An AESI is an AE of scientific and medical concern specific to the Sponsor's product(s).
 
The reporting requirements from the investigator to the Sponsor for an AESI will be the same as the reporting requirements for an SAE.

Adverse Device Effect (ADE)	Adverse event related to the use of an investigational medical device.
Serious Adverse Event (SAE)	
Adverse event that:
 
 a. Led to death. b. Led to serious deterioration in the health of the subject, that either resulted in. c. A life-threatening illness or injury. d. A permanent impairment of a body structure or a body function. e. Led to unplanned in-patient or prolonged hospitalization. f. Medical or surgical intervention to prevent life-threatening illness or injury or permanent impairment to a body structure or a body function. g. Led to fetal distress, fetal death or a congenital abnormality or birth defect. 
NOTE: Planned hospitalization for a pre-existing condition, or a procedure required by the CIP, without serious deterioration in health, is not considered a serious adverse event.

Serious Adverse Device Effect (SADE)	Adverse device effect that has resulted in any of the consequences characteristic of a serious adverse event.
Unanticipated Serious Adverse Device Effect (USADE)	Serious adverse device effect, which by its nature, incidence, severity, or outcome has not been identified in the current version of the risk analysis report.

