6.2.7.2 Sponsor's Responsibilities

All AEs will be reported annually to competent authorities in accordance with local regulations. All unanticipated adverse device effects (UADEs) will be reported within 10 calendar days of the event. Cochlear Americas or its designee will notify all participating Investigators of any new information that alters the current risk-benefit assessment of the study device or that would be sufficient to consider changes in management of the Nucleus cochlear implant or in the overall conduct of the trial.

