7.2 Anticipated adverse device effects

Just like any surgical treatment, Osia surgery is not free of risks. Risks associated with the implantation and use of the Osia System cannot be completely eliminated. General risks associated with surgery under general or local anesthesia apply, and as with any surgical procedure, there is always a risk that unanticipated complications may occur. These risks are expected to be similar for the Osia System as for traditional Baha surgery with the Baha Connect and Baha Attract Systems and the procedure for implanting the Cochlear Implants systems [Freedom Cochlear Implant platform (CI24RE) and Codacs® System].

Postmarket surveillance information is collected and those findings relevant for the Osia System is presented below:

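### Unanticipated serious device effects are defined in two unreconciled ways, and the definition that triggers prompt reporting has two conflicting 10-day clocks

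*Protocol*

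**What the plan says.** The definitions table in protocol section 6.2.1 lists the USADE, a serious adverse device effect "which by its nature, incidence, severity, or outcome has not been identified in the current version of the risk analysis report". The abbreviation list carries the same term. The bibliography and the two appendices do not include a risk analysis report.

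Section 6.2.6 brings in another term, the UADE, by quoting a US regulation. Its first limb covers a serious effect, life-threatening problem or death that "was not previously identified in nature, severity, or degree of incidence in the investigational plan or application", with supplementary plans and applications included. Its second limb adds "or any other unanticipated serious problem associated with a device that relates to the rights, safety, or welfare of subjects". UADE is in neither the table nor the abbreviation list.

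The reporting rules use UADE only. Under 6.2.6 the sponsor investigates once an investigator notifies it of a UADE, and the authority, ethics committees and investigators "will be notified within 10 working days after the sponsor first receives notice of the effect". The same section says that "only unanticipated adverse device effects will be reported promptly following occurrence", and that annual progress reports cover SAEs and AEs. Section 6.2.7.2 then states: "All unanticipated adverse device effects (UADEs) will be reported within 10 calendar days of the event".

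**The concern.** The investigator has to recognise a UADE before the sponsor's prompt action can begin. The place where an investigator would look up the definition, the table in 6.2.1, gives a different term, a different yardstick and a slightly different set of criteria. It also points to a document that the protocol does not supply and whose content may change during the study. Nothing says whether the two terms are meant to be the same.

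What is at stake is which serious device effects are escalated on a day count in a study of up to 20 children whose primary objective is the type and severity of adverse events. Separately, a sponsor that correctly identifies a UADE finds two deadlines that differ in both unit and starting point.

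**Working it through.** The protocol states no figure for this point that could be reproduced, so the check sets the sections side by side and then compares the two clocks.

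**Step 1: the two definitions**

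| | USADE (6.2.1) | UADE (6.2.6) |
|---|---|---|
| Reference | Risk analysis report in its current version | Plan or application, including supplements |
| Criteria | Nature, incidence, severity, outcome | Nature, severity, degree of incidence |
| Catch-all limb | None | Yes, with no reference document named |
| In the table and abbreviation list | Yes | No |
| Reporting rule attached | None | 6.2.6 and 6.2.7.2 |

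**Step 2: where a serious device effect falls**

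1. Identified in both references, on all criteria: neither term applies.
2. Identified in neither: both terms apply, and the UADE rule requires prompt notification.
3. In the risk analysis report but not in the plan or application: UADE, not USADE. The text requires prompt notification. The risk is a site that reads only the table and treats the effect as anticipated.
4. In the plan or application but not in the risk analysis report, or identified there in nature, severity and incidence but with a new outcome: USADE, but not UADE under the first limb. It reaches the day-count rule only if the catch-all limb covers it, and that limb names nothing against which to judge.

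The definitions diverge in cases 3 and 4. Case 4 is a gap in the text itself. Case 3 is a risk of misreading.

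**Step 3: the two clocks for a UADE**

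Let d be the number of calendar days from the event to the sponsor's first notice. I find no day count in the protocol for that step, so d is an assumption. With a five-day week, no public holidays and notice on a weekday, 10 working days span two weekends: 10 + 4 = 14 calendar days.

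- Deadline under 6.2.6, counted from the event: d + 14
- Deadline under 6.2.7.2, counted from the event: 10
- Difference: (d + 14) − 10 = d + 4

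| d (illustrative) | 6.2.6 | 6.2.7.2 | Difference |
|---|---|---|---|
| 0 | day 14 | day 10 | 4 days |
| 5 | day 19 | day 10 | 9 days |
| 10 | day 24 | day 10 | 14 days |

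For d above 10 the second deadline passes before the sponsor has heard of the event. Notice on a Saturday or Sunday shortens the first span to 13 or 12 days. Public holidays lengthen it.

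**The case against.** The strongest reply is that the text gives one answer for every event. Both day-count rules name UADE and neither names USADE, so a careful reader applies the 6.2.6 test and USADE is merely an unused definition. This stands in part. A reader might infer that the protocol puts the same effect both inside and outside the 10-day rule. It does not; that happens only if someone substitutes the USADE test. The catch-all limb may also bring many USADEs back in, and the application may contain the risk analysis report, which would narrow the difference. Neither document is available to check. What remains is that the table directs the site to the test without consequences, and that nothing settles case 4.

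Other stronger readings also lack support:

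- *The anticipated/unanticipated call alone decides between days and a year.* Section 6.2.3 asks for events of special interest, including revision surgery and severe soft tissue complications at the implant site, as soon as possible. Section 6.1 wants deficiencies that could have led to an SAE reported at once. Sections 6.2.7.2 and 9.3 provide for passing on new safety information. None of these sets a day count, but together they mean the annual report is not the only alternative.
- *Section 7.2 omits hearing-threshold shifts although 6.2.4 monitors them, so these would be reported late.* Section 7.2, introduced by "Postmarket surveillance information is collected and those findings relevant for the Osia System is presented below", does omit them. But an omission from the plan makes a serious device-related shift more likely to count as a UADE. Section 6.2.4 by itself classes such shifts only as AEs.
- *A USADE or UADE count could not be reproduced.* The protocol plans no such count.
- *Most or all children could be implanted before a first report.* The timetable in 10.8 dates first visits, not surgeries, and the inference ignores the other routes above.

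**Conclusion.** The inconsistency is real and should be corrected. Two unlinked definitions use different references and criteria. The one in the table has no reporting rule and relies on a document not supplied with the protocol. An effect can be a USADE without clearly being a UADE. In addition, 6.2.6 and 6.2.7.2 contradict each other on the deadline, by d + 4 calendar days under the weekday, five-day-week, no-holiday assumption.

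No estimate, sample size or hypothesis is affected, and the protocol has no formal hypothesis. The effect is on the escalation of serious device effects. How many events would be affected cannot be judged without the application and the risk analysis report. The document does not settle which deadline applies under regulation, or which of the two definitions was intended.

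**What to change.** Reconcile 6.2.1, 6.2.6, 6.2.7.2 and the abbreviation list together:

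- Keep one term, define it once in the table, and use it in every reporting rule.
- Name one reference, with its version and date, and give it to the site. It must be consistent with the plan-or-application wording that 6.2.6 quotes. If the risk analysis report is meant to be part of that reference, say so and cite it.
- State whether a new outcome makes an effect unanticipated.
- State one notification clock, with its unit, its starting point and its recipients.
- Have the site send every serious device effect to the sponsor promptly, and have the sponsor make the anticipated/unanticipated call against the named reference.

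The cost is wording in those sections and a few more site-to-sponsor reports. No new assessments of the children are needed.

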6.2.7 Assessment and Reporting of Adverse Events

6.2.7.1 Investigator’s Responsibilities

Throughout the course of the study, all efforts will be made by the Investigators to remain alert to possible AEs. The first concern will be the safety and welfare of the subject and for providing appropriate medical intervention, as indicated. Detailed information regarding adverse events (AEs) will be recorded by the Investigator at the time an adverse event occurs using CRFs for the study. All adverse events will be recorded from the day of enrollment (Day 0) to termination of study, approval of the product, or when the subject exits the study, whichever is the last, even if the event was acknowledged as a risk factor in the *Informed Consent Form*.

AEs will be recorded on the CRF will include the following information:

- Date of onset
- Date reported to the clinic
- Description of the AE
- Seriousness
- Investigator’s assessment of the relationship of the AE to the device and/or procedure
- Treatment
- Outcome

6.2.7.1.1 Adverse Event Follow-up

All AEs must be followed until resolution, or the condition stabilizes. The Investigator is responsible to ensure that follow-up includes any supplemental investigations as may be indicated to elucidate as completely as possible the nature and/or causality of the AE. This may include additional laboratory tests or investigations, or consultation with other health care professionals. Cochlear or its designee may request that the Investigator perform or arrange for the conduct of supplemental measurements and/or evaluations. AE follow up information will be recorded using the CRFs for the study.

6.2.7.2 Sponsor's Responsibilities

All AEs will be reported annually to competent authorities in accordance with local regulations. All unanticipated adverse device effects (UADEs) will be reported within 10 calendar days of the event. Cochlear Americas or its designee will notify all participating Investigators of any new information that alters the current risk-benefit assessment of the study device or that would be sufficient to consider changes in management of the Nucleus cochlear implant or in the overall conduct of the trial.

6.3 Concomitant medication(s) and treatment(s)

All medications and treatments given, whether or not to treat AEs/ADEs, must be recorded in the appropriate section of the case report form. Medication given as standard of care in connection with surgery should not be recorded in the CRF.

7 RISK AND BENEFITS OF THE INVESTIGATIONAL DEVICE(S) AND THE CLINICAL INVESTIGATION

7.1 Anticipated clinical benefits

The Osia System is an extension of the existing approved Baha product family and is expected to provide the same benefits as these systems in terms of hearing restoration. In addition, the Osia System may provide additional advantages as it combines benefits from both a percutaneous (skin-penetrating) and transcutaneous Baha system.

The Osia System provides efficient sound transmission through direct bone conduction, similar to a percutaneous implant. Direct bone conduction through a transducer that is directly coupled to the bone is currently only achieved with the percutaneous Baha Connect System. With the active transcutaneous Osia System, the actuator is directly attached to the bone via the osseointegrated BI300 Implant underneath the skin, thus eliminating any loss of energy in the sound vibrations through the skin. Hence, it is expected that efficiency of sound transmission will be on a par with a percutaneous system.

The Osia System provides the cosmetic benefits of a transcutaneous system, such as the Baha Attract System. A percutaneous implant is often seen as a barrier and is rejected by candidates due to cosmetic concerns. A transcutaneous system, without an abutment protruding through the skin, may be perceived as a more aesthetic option.

The Osia System, like the Baha Attract System, may significantly reduce the risk of implant site infections, and eliminate the need for daily maintenance care. For the transcutaneous Baha Attract System and Osia System, the implant site is sealed and does not provide a direct path for infections. Skin irritation and/or infection requiring treatment and/or precluding the use of the sound processor are relatively frequent for percutaneous devices due to the exposed abutment and daily site care is required to maintain a reaction-free skin penetration. Some patients are not able—for medical or other reasons—to perform the daily implant site care that the skin-penetration requires.

The Osia System may be associated with a significantly lower risk of osseointegration failure than for the percutaneous Baha Connect System. This risk is expected to be similar to that of the Baha Attract System, which also uses the osseointegrated BI300 Implant. According to the latest post market surveillance reports^{13, 14} no osseointegration failures have been reported to Cochlear's complaints handling system, nor in the review of scientific literature for the Baha Attract System¹⁵.

7.2 Anticipated adverse device effects

Just like any surgical treatment, Osia surgery is not free of risks. Risks associated with the implantation and use of the Osia System cannot be completely eliminated. General risks associated with surgery under general or local anesthesia apply, and as with any surgical procedure, there is always a risk that unanticipated complications may occur. These risks are expected to be similar for the Osia System as for traditional Baha surgery with the Baha Connect and Baha Attract Systems and the procedure for implanting the Cochlear Implants systems [Freedom Cochlear Implant platform (CI24RE) and Codacs® System].

Postmarket surveillance information is collected and those findings relevant for the Osia System is presented below:

7.2.1 Osia Sound Processor

The Osia SP has identical hardware as the CP950 Sound Processor for Cochlear Implants, but with Osia specific firmware. Since the CP950 Sound Processor is recently new and no post-market surveillance data is yet available, the safety data is based on literature reviews and reviewing the complaints and adverse event (reportable complaint) trending rates for the predicate devices and for the Baha Attract System. The most common complaint is magnetic retention issues of the sound processor. Skin irritation for predicate device is not reported as an issue. For the Baha Attract system, skin irritation is possible but not reported as a serious problem and often solved by adjusting the magnet strength. Potential skin irritation problems will be managed by a combination of adjustment of magnet strength and/or use of the Softwear Pad.

7.2.2 Receiver-stimulator (CI24RE)

During the period 1 July 2009 to Dec 2015, the cumulative number of registered implant surgeries (IS) with CI24RE implants was 153,040 (14,402 surgeries during the last year). Of the total number of registered implant surgeries, 80 reportable complaints (0.052% of total IS) have been attributed to the receiver-stimulator. Overall, reportable complaints in the category 'Reliability/quality/defect' occurred at an average rate of 0.006% of the total number CI24RE implant surgeries per month. The complaints are being monitored and there is no upward trend. The majority of complaints in the category "Medical/surgical issue" have been coded as "Other medical", "Skin flap infection" and "Medical/surgical issue (recipient related)" and the maximum harm for a complaint that was attributed to the device was revision surgery to explant the device.

Based on the post-market surveillance activities performed, the CI24RE series of implants are considered to be performing in the field within acceptable limits and expectations. The Clinical Evaluation Report (411167, Clinical Evaluation Report Nucleus CI24RE Cochlear Implants) provides clinical evidence to establish the acceptability of the risk benefit analysis of the CI24RE Series of Implants ¹⁶.

7.2.3 Codacs

During the period 18 October 2013 to 31 October 2015, the cumulative number of registered implant surgeries with Codacs DI110 implant and DF110 Fixation System was 65 (39 during the last year). No reportable complaints were attributed to the receiver-stimulator or the lead. The number of reportable events related to medical/surgical issues or no-fault-found was 2 (3.1%). Based on the post-market surveillance activities performed, the Codacs DI110 implant and the Codacs DF110 Fixation System are considered to be performing in the field within expectations (D701349, Post Market Surveillance Report, Codacs DI110 implant and DF110 Fixation system) ¹⁷.

7.2.4 BI300 Implant with the Baha Connect System

Since launch in 2010 to Oct 2015, 55,341 BI300 implants (including abutment) have been sold with a reported monthly complaint rate around 0.1-0.2%. The complaint relevant to the Osia System is BI300 implant loss. The rate of implant loss for the Baha Connect System is around 1%. The overall complaint rates and reportable events are well below the pre-defined escalation threshold ¹⁴.

7.2.5 BI300 Implant with the Baha Attract System

During the period Aug 2013 to Jan 2017, approximately 11,000 BIM400 (Baha Attract Implant magnet including BI300) have been sold globally. The most commonly reported symptoms are skin reactions and/or pain around the implant magnet and magnet retention issues with an overall rate of up to 2%. The symptoms are usually reported to be mild and treated by adjusting Sound Processor (SP) Magnet strength.

No cases of implant loss due to osseointegration failure have been confirmed. The overall complaint rates and reportable events are well below the pre-defined escalation threshold (D784107, Post Market Surveillance Report, Baha Attract, November 2015) ¹³.

7.3 Risks associated with participation in the clinical investigation

Risks associated with participation in this study are anticipated to be similar for a child in relation to the adult population. The investigational device incorporates several components from already FDA and Health Canada approved products. There is no guarantee that the Osia Implant will not cause any adverse device events. The Osia Implant is expected to have a lifetime of about 10 years. As with any new surgical product and medical device, there is a risk that Unanticipated Adverse Event may occur. The subjects will be closely monitored in the investigation and instructed to contact the responsible investigator if they experience any untoward effect. In the worst-case

scenario, the patient would need a revision surgery to remove the Osia Implant. The subject will then end participation in the clinical investigation and follow normal clinical care and follow-up.

